5.4 PRIM-DJ2727 Dispense and Handling

After randomization, PRIM-DJ2727 capsules will be delivered to the clinic site in two single dose standard opaque plastic containers for Day 1 and Day 2 treatment. Two single dose containers will be labeled with the study drug, the name of the PI, number of capsules, lot number, date, and instructions (see CMC protocol for label details). Study personnel delegated by the investigator will open the day 1 dose container and administer capsules to subject with water. Delegated study personnel will dispense day 2 dose container to subject with an ice-pack to take home. Subject will be instructed to keep the day 2 dose container in refrigerator at home.

6. TREATMENT FAILURES AND RETREATMENT

Treatment failure is defined as the presence of diarrhea (passage of ≥ 3 watery stools per 24-hour period for two consecutive days) and *C. difficile* toxin A/B positive stool within 60 days of FMT treatment and receipt of anti-*C. difficile* antibiotics.

If diarrhea (passage of ≥ 3 watery stools per 24-hour period for two consecutive days) occurs and CDI recurrence is suspected, subjects should inform study team and be recommended to contact their physician to perform a stool test for *C. difficile*. EPDL will test scheduled stool specimens and any unscheduled illness stool submitted up to days 60-70 after treatment for *C. difficile* toxins A/B in weekly batches but this should not delay treatment. If the test is positive, they should be treated by their physician. The Principal Investigator will be available for consultation with the attending physician. Subjects who are determined treatment failures by the investigator will not be followed further for clinical parameters. They will be offered FMT retreatment with maximum dose (200g) from a different donor product if the subject and their physician wish to pursue this treatment. After at least 10-20 days of anti-CDI antibiotics (vancomycin or fidaxomicin) subjects will be eligible for second FMT after 24-96 hour washout. If there is a delay between completing treatment and second FMT, the subject will receive at least four days of vancomycin or fidaxomicin prior to FMT (PI can call in prescription if needed) to complete the treatment 24-96 hours before second FMT. Subjects will be recommended to follow a clear liquid diet the entire day before retreatment clinic visit. Bowel preparation and Imodium will not be required before retreatment. During retreatment clinic visit, vital signs and weight will not be assessed and subjects will be observed for 30 minutes after dosing.

Retreatment Dosage: Day 1 (Clinic Visit)

- Subjects are recommended to continue clear liquid diet until 1 hour after retreatment.

- Perform urine pregnancy test on all female subjects of childbearing potential prior to FMT administration.
- Administer Day 1 dose and dispense Day 2 dose.
- Observe the subject for 30 minutes after dosing.
- Remind subject that Day 2 dose should be taken the next morning on empty stomach with water and release the subject.

Retreatment Dosage: Day 2 (Phone Visit)

- Ask that subject has taken the Day 2 dose.
- Ask for any adverse events since Day 1 assessment.
- A form letter may be faxed or emailed to subject's physician about FMT completion.

Subjects will be withdrawn from the study after retreatment Day 2 phone visit. After any second FMT, the subjects' own physician will monitor and manage the patients' illnesses.

If a subject experiences diarrhea and C. difficile toxin A/B test is negative, then the subject is not considered a treatment failure as the presence of C. difficile was not established. The study investigator will evaluate the patient's clinical picture and help decide whether the subject remains on the study. The PI will be available to discuss with subject's physician about continuing illness to arrive at the best outcome for the subject.

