3. STUDY DESIGN

This is a single center, randomized, parallel assignment, double-blinded, safety and

efficacy study to be conducted in subjects with recurrent CDI. Approximately 360 subjects will be enrolled in the study and randomized at 1:1:1:1 ratio to receive lyophilized donor intestinal bacteria with various doses (group 1 receiving healthy microbiota collected from 50g stool for 2 consecutive days; group 2 receiving healthy microbiota collected from 100g stool on the 1st day of treatment and from 50g stool on the 2nd day of the treatment; group 3 will receive healthy microbiota collected from 100g stool for 2 consecutive days using bowel prep and Imodium. An unblinded group 4 will receive healthy microbiota collected from 100g stool for 2 consecutive days without using bowel preparation and Imodium. All subjects will be followed for approximately 180-200 days following FMT treatment for safety.

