3.4 Data Safety and Monitoring Board

A committee of 3 faculty level people will serve as the DSMB reviewing primary and

secondary parameters and data from the study. Safety will be the greatest concern. The DSMB has the capacity to stop the study. The Board will meet at least three times during the study: At the study beginning; after 8-10 patients in each group have been studied and at the completion of the study (all subjects reached 180-200 days follow-up after FMT).

Professional	Name
Pharmacist	[name]
Epidemiologist	[name]
Clinical Infectious Diseases Specialist	[name]

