4.6 Handling of Withdrawals and Discontinuation of Treatment

Subjects are free to withdraw at any time. The primary reason for withdrawals from the study will be recorded in the study exit form. Subjects who withdraw or are withdrawn will be encouraged to complete an Early Termination Phone Visit to assess for AEs. Subjects who withdraw will be discontinued from all study procedures.

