9. ASSESSMENT OF SAFETY AND EFFICACY

9.1 Assessment of Safety (Definition)

9.1.1 Adverse event:

Any untoward medical occurrence associated with the use of PRIM-DJ2727 whether or not considered drug related, and can therefore be

- Any symptom not previously reported by the subjects (medical history/pre-treatment diary). Wherever possible, a specific disease rather than individual associated signs and symptoms should be identified by the investigator. However, if an observed or reported sign or symptom is not considered a component of a specific disease by the investigator, it should be recorded as a separate adverse event.
- Clinical worsening of baseline parameters according to subject.
- A condition felt to be possibly related to treatment first detected or diagnosed after study drug administration

All adverse events (AEs) that occur within 180-200 days after treatment will be recorded as indicated above. Recurrence of CDI is not to be recorded as an adverse event unless hospitalization ≥ 24 hours is required for management, then recorded as serious adverse event.

9.1.2 Suspected adverse reaction:

Any adverse event for which there is a reasonable possibility that the study drug caused the adverse event. For the purposes of IND safety reporting, "reasonable possibility" means

there is evidence to suggest a causal relationship between the drug and the adverse event.

9.1.3 **Serious adverse event:**

Any adverse event or suspected adverse reaction is considered serious if in the view of the investigators it results in any of the following outcomes:

- Death
- Life-threatening adverse event
- Hospitalization \geq 24 hours
- Prolongation of existing hospitalization
- Substantial disruption of the ability to conduct normal life functions
- Congenital abnormally/birth defect
- Important medical events that jeopardize the patient, such as allergic bronchospasm requiring intensive treatment
- Persistent or significant incapacity or substantial disruption of the ability to conduct normal life functions

An emergency room visit without hospital admission will not be recorded as a serious adverse event (SAE) under this criterion, nor will hospitalization for a procedure scheduled or planned before signing of informed consent.

Death and life-threatening AEs possibly related to the study are reported by study coordinator or investigator within 24 hours to the IRB. Other SAEs potentially related to the study will be reported to the IRB within 7 days.

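### Retreated failures leave the study after the retreatment Day 2 call although all subjects are to have 180-200 days of safety follow-up, so scheduled safety contact depends on efficacy

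*Combined protocol and SAP*

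**What the plan says.** **Exit rule.** Section 6 offers a second FMT to treatment failures, "if the subject and their physician wish to pursue this treatment". For those who take it, "Subjects will be withdrawn from the study after retreatment Day 2 phone visit", and their own physician takes over monitoring. Failure is an efficacy outcome, judged within 60 days of the first FMT. Section 6, repeated in Section 8.5, also says: "Subjects who are determined treatment failures by the investigator will not be followed further for clinical parameters". The protocol does not define clinical parameters.

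**Safety follow-up.** Section 3: "All subjects will be followed for approximately 180-200 days following FMT treatment for safety". Section 9.1.1: "All adverse events (AEs) that occur within 180-200 days after treatment will be recorded as indicated above". Section 9.6 obliges the investigator to document and follow serious adverse events and events of special interest over the same 180-200 days. None of the three makes an exception for retreated subjects.

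**Contrast within the plan.** Subjects who take a systemic antibiotic within 60 days are removed from efficacy, but Sections 4.8 and 7.3 keep them on phone visits and diaries to Day 180-200 for safety.

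**Analysis.** Section 10.2.3 puts safety into both primary analyses (groups 1-3, and group 3 against group 4) and includes everyone who started the procedure. Section 10.2.5 summarises adverse events as crude counts and percentages. It says nothing about unequal follow-up or events after retreatment.

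**The concern.** A site cannot both withdraw a retreated subject after the Day 2 call and give that subject the scheduled safety contacts to Day 180-200. Because only failures are retreated, the length of planned safety contact depends on how well the assigned treatment worked. The retreated subjects remain in the denominator of a crude percentage, so a group with more failures has fewer chances to record an event.

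Two things are at stake. The first is the late safety record. Safety is the first-listed primary endpoint. Retreated subjects receive a second product from a different donor, and scheduled contact ends one day after its first dose. The halting criteria in Section 9.10 turn on possibly related serious events and suspected pathogen transmission, and after that call no scheduled contact would bring either to light. The second is the comparison between groups, which could favour the less effective group for a reason unrelated to safety.

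**Working it through.** **Plan's own figure.** Section 7.1 gives participation of up to 216 days: 14 (enrollment) + 2 (treatment) + 200 (follow-up) = 216. It reproduces.

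**Inputs from the documents.** There are 90 per group. Assumed efficacy (Section 10.2.2) is 70%, 80%, 88% and 80% for groups 1-4, so the failure proportion f is 0.30, 0.20, 0.12 and 0.20.

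**Inputs assumed.** Retreatment uptake u is 0.5-1. Exit day d is 20-120. Event risk R by Day 180 is 30%, equal in all groups. The documents give none of these. On exit day, Section 6 sets a minimum but no maximum interval before retreatment ("If there is a delay between completing treatment and second FMT" it adds further antibiotic days). With no delay, a very early failure could exit at about Day 14. A failure on Day 60 with 20 antibiotic days and 4 washout days would exit at about 60 + 20 + 4 + 1 = Day 85.

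**Expected failures**, 90 × f: 27, 18, 10.8 and 18. The total is 73.8 of 360.

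**Day 180 contact missing by rule**, u × f: 15-30% in group 1, 10-20% in groups 2 and 4, 6-12% in group 3.

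**Artificial gap, constant hazard.** λ = -ln(1 - 0.30)/180. Recorded risk = (1 - uf)R + uf(1 - exp(-λd)).

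| u | d | Group 1 | Group 3 | Gap (points) |
|---|---|---|---|---|
| 1 | 20 | 22.2% | 26.9% | 4.70 |
| 1 | 60 | 24.4% | 27.7% | 3.38 |
| 1 | 120 | 27.3% | 28.9% | 1.59 |

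The gap is proportional to u, so at u = 0.5 it is 2.35, 1.69 and 0.80. Group 3 against group 4 scales by 0.08/0.18, which gives 0.35-2.09 points. With R = 10% the gap between groups 1 and 3 is 0.3-1.6 points.

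**Artificial gap, early events.** If a share s of the risk has accrued by exit, the gap is u × 0.18 × R × (1 - s). For s = 0.75-0.90 this is 0.27-1.35 points.

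**Yardstick.** The 95% half-width for a difference at an assumed 25% event rate and 90 per group is 1.96 × √(2 × 0.25 × 0.75/90) = 12.7 points.

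**If failures carry more risk.** With u = 1 and 1.5-2 times the hazard in failures, the true excess in group 1 over group 3 is 0.18 × (1 - 0.7^1.5 - 0.30) to 0.18 × (1 - 0.7^2 - 0.30), or 2.1-3.8 points. The crude table would show -4.4 to +1.4, and a Kaplan-Meier estimate censored at retreatment 0.2-2.7. The sign of the net distortion is therefore not certain.

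**The case against.** The best defence is that Section 6 is a specific, deliberate rule and the follow-up statements are general. Section 7.1 says participation lasts up to 216 days, Section 3 says approximately, and Section 4.5 lets the investigator withdraw a subject for any reason. The second FMT is not randomised and has one total dose whatever the original group, so ending the randomised safety comparison at retreatment is defensible. The bias estimate rests on assumptions, and its top end needs every failure to be retreated and gone by Day 20. At 25% uptake the gap is 0.4-1.2 points. Solicited symptoms are collected only to Day 60 for everyone, which makes a constant hazard to Day 180 a poor fit. Section 10.2.5 names no safety test.

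Much of this stands on size. It does not remove the conflict: a standing rule triggered by the efficacy outcome is not a case-by-case withdrawal, and the plan nowhere says that its safety comparison stops at retreatment.

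A reader might also infer more than the text supports:

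- **That Section 4.6 ends all procedures for these subjects.** Its sentence "Subjects who withdraw will be discontinued from all study procedures" covers those who withdraw. The sentence before it separately names those who are withdrawn. Section 6 carries the point without it.
- **That Section 3.4 creates a follow-up requirement.** The words "at the completion of the study (all subjects reached 180-200 days follow-up after FMT" date the last DSMB meeting. Any ordinary withdrawal would also break them.
- **That the duty to follow serious events lapses, leaving only Section 9.8.** Section 9.8 concerns the time after the study's conclusion or a subject's completion. The Section 9.6 duty still stands on its face. What is missing is scheduled contact to support it, beyond a single encouraged early-termination call.
- **That failures who decline retreatment also lose safety follow-up.** The undefined term clinical parameters may end efficacy follow-up only.

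**Conclusion.** The conflict between Section 6 and Sections 3, 9.1.1 and 9.6 is in the text and needs no assumption. For retreated subjects, scheduled safety contact ends early because of an efficacy outcome, and on the plan's assumptions the pool of failures is 2.5 times as large in group 1 as in group 3 (27 against 10.8).

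It would be tempting to conclude that the primary safety comparison is materially biased in favour of the least effective dose. The documents do not support that. Uptake, exit day and event risk are not given, the plausible distortion is well inside the sampling error of about 13 points, and its direction is uncertain if failures differ in risk. The real cost is late safety information, including after a second FMT, together with an unstated rule for handling those events. Severity: minor to moderate.

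**What to change.** 1. **Reconcile Sections 6 and 8.5 with Sections 3, 9.1.1 and 9.6.** Define clinical parameters. State that failures, retreated or not, leave efficacy follow-up only and stay on the already scheduled safety phone visits to Day 180-200 after the first FMT, as Sections 4.8 and 7.3 do for antibiotic users. The retreatment rule itself is unchanged.
2. **Add a rule to Section 10.2.5.** Tabulate events before and after retreatment separately. Compare randomised groups in two ways: censored at retreatment, and on all events as randomised. Note that censoring assumes failures have the same event risk, and that the all-events comparison includes the effect of the second FMT.

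**Cost.** A short amendment, one extra table and one extra analysis. Exit at Day 120 leaves one call (Day 180), and exit at Day 20 leaves four (Days 30, 60, 90 and 180). For up to 73.8 failures that is 73.8 × 1 to 73.8 × 4, about 74-295 calls if none would otherwise be called. The number is lower if decliners are already followed for safety, and slightly higher for anyone leaving before the Day 7 or Day 14 call. The documents give no budget for this.

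**Limit.** The clock runs from the first FMT, so someone retreated near Day 85 would have only about 95-115 days (180 - 85 to 200 - 85) of contact after the second.

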4.5 Subject Withdrawal or Termination

Subject's participation is considered complete approximately 180-200 days after FMT procedure; however, subjects may withdraw from the study at any time for any reason, without any consequence. In addition, a subject may be withdrawn from the study by the investigator for any reasons including the following:

1. Lost to follow-up
2. Adverse Event (AE) or Serious Adverse Event (SAE)

3. Protocol violation/non-compliance
4. Subject decision to withdraw consent
5. Investigator decision to terminate the study

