10.2.3 Analysis Populations

Two primary analyses will be performed:

- 1) Analysis for safety and efficacy between three groups (1-3) receiving varied doses of lyophilized product generated from stool (50g for both treatment days; 100g on the first treatment day and 50g on the second treatment; 100g for both treatment days)
- 2) Analysis for safety and efficacy between two groups (3 and 4) with and without bowel preparation and Imodium receiving same high doses of lyophilized product (100g for both treatment days).

- All analyses will be conducted using the intent-to-treat population. Intent-to-treat is defined as all subjects who have started the procedure.
- Listings and summary tables with descriptive statistics will be prepared for demographic data (gender, date of birth, race/ethnicity), and medical history data.

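### Section 6 lets a subject with toxin-negative diarrhea be taken off study by unstructured judgement inside the 60-day primary window, and the plan does not say how the missing outcome is scored

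*Combined protocol and SAP*

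**What the plan says.** Section 6 defines failure by three elements together: diarrhea, a "toxin A/B positive stool within 60 days of FMT treatment", and receipt of anti-*C. difficile* antibiotics. For diarrhea with a negative test, "then the subject is not considered a treatment failure as the presence of C. difficile was not established". The next sentence has the investigator look at the clinical picture and "help decide whether the subject remains on the study". No criterion for staying or leaving follows.

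Four other sections determine what happens next:

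- **Section 4.5:** "a subject may be withdrawn from the study by the investigator for any reasons including the following". The list that follows is not exhaustive.
- **Section 4.6:** "Subjects who withdraw will be discontinued from all study procedures". Those who leave, by either route, are encouraged to complete one early-termination call, whose stated purpose is adverse events.
- **Sections 7.2 and 7.3:** recurrence is evaluated at each follow-up contact for 60 days, and stools submitted up to Days 60-70 are tested for toxin.
- **Section 10.2.3:** "Intent-to-treat is defined as all subjects who have started the procedure". Group 3 versus group 4 is one of the two primary analyses.

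The synopsis and section 3 make groups 1-3 blinded and group 4 unblinded.

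**The concern.** The two doses are taken on consecutive days. Once both are taken, removing a subject changes no study treatment and only stops observation. Here the stop is triggered by diarrhea, which is one of the three elements of the primary efficacy event, and it can happen while the 60-day window is still open. That is loss to follow-up related to the outcome.

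Two things are at stake. The first is the failure count in each arm, because a recurrence after removal is never ascertained. The second is the comparison of groups 3 and 4, because the people making the retention decision can know who is in group 4. Removal also cuts short the adverse-event follow-up to Days 180-200, and safety is a primary endpoint.

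**Working it through.** **Step 1. Follow one subject through the text.** Take a subject with diarrhea and a negative toxin test at the Day 7 contact.

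- *Kept on study:* the Day 14, 30 and 60 contacts and stool tests go ahead. Section 6 clears the toxin-negative episode only, so a later episode with a positive test and anti-*C. difficile* treatment still counts as a failure.
- *Taken off study:* 60 − 7 = 53 days of the window are unobserved. Section 4.6 offers one adverse-event call and does not seek the Day-60 CDI outcome.
- *Analysis:* the subject started the procedure and so stays in the intent-to-treat population. No section says whether the unobserved outcome is a success, a failure or missing.

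**Step 2. Inputs for size.** From section 10.2.2: 90 per group, with assumed efficacy of 88% in group 3 and 80% in group 4. Expected failures are 0.12 × 90 = 10.8 and 0.20 × 90 = 18.0, a gap of 7.2 failures (8 points). The documents give no rate of toxin-negative diarrhea, of removal, or of later recurrence. Three **assumptions** stand in: 10% to 20% of subjects have toxin-negative diarrhea by Day 60, half of them are removed, and 30% of those removed would later meet the failure definition.

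**Step 3. Failures not observed, per group.**

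- Low: 90 × 0.10 × 0.5 × 0.3 = 1.35, which is 1.35 / 90 = 1.5 points.
- High: 90 × 0.20 × 0.5 × 0.3 = 2.7, which is 2.7 / 90 = 3.0 points.

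**Step 4. Effect on group 3 versus 4 if removed subjects are scored as non-failures.**

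| Where removal falls | Apparent gap | Change as share of 8 points |
|---|---|---|
| Equal counts in both arms | 8.0 points | 0% |
| Group 4 only | 6.5 to 5.0 points | 1.35/7.2 = 19% to 2.7/7.2 = 38% |
| Group 3 only | 9.5 to 11.0 points | 19% to 38%, opposite sign |

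In the group 4 only case, pairwise power at 90 per group falls from about 31% to about 23% (81.5% apparent efficacy in group 4) or 16% (83%).

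**Step 5. Effect if they are scored as failures.** The error in each arm's rate reverses. The removed subjects number 4.5 to 9 per group, of whom 1.35 to 2.7 would truly fail. The excess failures are 4.5 − 1.35 = 3.15 to 9 − 2.7 = 6.3, so efficacy in that arm is understated by 3.5 to 7.0 points.

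**Step 6. False-positive check.** Take two arms of 90 with the same true efficacy of 80%. If one arm alone misses 10% or 20% of its failures and these count as non-failures, simulation gives a rejection rate of about 6% or 10% instead of the nominal 5%. The losses in step 3 are 1.35/18 = 7.5% to 2.7/18 = 15% of group 4's expected failures, so they lie around the lower end of that range.

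**Step 7. Plausibility of the inputs.** They imply 9 × 0.3 = 2.7 to 18 × 0.3 = 5.4 failures per group that follow a toxin-negative episode. Against 10.8 expected failures in group 3, that is 25% to 50% of them. Nothing in the documents supports so large a share, so the upper end is an illustration and not an estimate.

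**The case against.** Several stronger readings are tempting, and the documents do not carry them.

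- *One negative test ends the matter.* Section 6 speaks of a negative test without giving a number. Sections 6 and 7.3 provide two routes to a test, the subject's physician and the study laboratory, and a retained subject can still fail later.
- *These are the highest-risk subjects.* This is a plausible inference with no figure behind it. Section 9.5 lists diarrhea as an anticipated event that need not be caused by FMT or CDI.
- *The rule inflates efficacy.* That requires scoring as non-failure, which is not stated. Step 5 shows the opposite result under the opposite rule.
- *Bowel prep and Imodium make the triggering diarrhea differ by arm.* Prep is taken on Day -1 and Imodium once around Day 1 (section 8.1). Section 9.5 places their expected effects between the day before treatment and one day after it, a small part of a 60-day window. What remains is that group 4 is unblinded, which makes differential removal possible but does not show it.
- *A fixed 19% to 38% of the group 3 versus 4 gap is lost.* That is the one-arm case only. Equal removal gives 0%.

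Three further points are fair. The section 6 decision is shared, since the investigator only helps decide. The sentence in section 4.6 that ends all procedures names subjects who withdraw, so applying it to removal by the investigator is a reading, although the preceding sentence covers both groups. And section 10.2.6 expects trends and not statistical significance, which lowers the weight of a small ascertainment loss.

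All of this limits the claim. None of it supplies a retention criterion, a Day-60 outcome after removal, or a scoring rule.

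**Conclusion.** The point holds as a design weakness that should be corrected. The plan states a discretionary removal rule tied to a component of its primary endpoint, inside the endpoint window, with one arm of a primary comparison unblinded. The scheduled contacts and tests that would avoid the loss are already in the plan.

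The direction of bias is not fixed, because the scoring of the missing outcome is not stated. The size cannot be derived from the documents. With non-failure scoring and the three assumptions in step 2, the distortion of the assumed 8-point gap between groups 3 and 4 is 0% to 38%, with 0% if removal is equal in both arms. Among the blinded groups 1-3 the decision cannot follow known dose, although the number of subjects facing it could differ if diarrhea differs by dose.

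**What to change.** 1. **Section 6.** Replace the sentence on remaining in the study with: *A toxin-negative diarrheal episode is not by itself a reason for removal from the study. The subject continues the scheduled calls and stool toxin tests to Day 60 and safety follow-up to Day 180-200, and any later episode meeting the failure definition within 60 days counts as failure.* Make this subject to the existing provisions for systemic antibiotic use (sections 4.8 and 7.3), treatment failure and retreatment (section 6), and withdrawal of consent.
2. **Section 4.5.** Make the investigator-withdrawal clause consistent with this. Otherwise the same discretion survives there.
3. **Section 10.2.3 or 10.2.6.** State how a dosed subject without a Day-60 outcome is scored in the intent-to-treat analysis, for example as a failure, with a sensitivity analysis under the opposite scoring. Step 5 shows that a scoring rule alone does not remove the error, so item 1 is the main repair.

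Clinical care of the diarrhea stays as written. The cost is a few sentences in three places. The calls and stool tests are already scheduled, and the planned sample size does not change.
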